While IV Cytoxan (CYC) administration per NIH protocol was the standard of care for the treatment of renal disease in SLE, the serious side effects led to a continued search for new approaches. Studies have shown that Mycophenolate Mofetil (MMF) provides comparable efficacy to IV CYC for both induction and maintenance with fewer side effects [13-17, 20]. MMF is an immunosuppressive agent that suppresses *de novo* purine synthesis by selectively inhibiting inosine-5'-monophosphate dehydrogenase. Unlike other cell types, lymphocytes are heavily dependent upon this mechanism for proliferation. As a result, MMF is capable of decreasing the proliferation of lymphocytes and the production of autoantibodies without the cytotoxic or mutagenic effects of CYC [18, 19]. Clinical trials comparing these two medications are discordant in their response rates but uniformly show them to be equivalent in efficacy. In the study conducted by Chan *et al.*, 95% of patients achieved clinical response (both complete and partial) with MMF (32 patients) and 90% with CYC (30 patients) [14]. In contrast, in the study by Ginzler *et al.*, only 52% responded to MMF (71 patients) and 30% to CYC (69 patients) [16]. The disparity observed between the Chan and Ginzler studies may be attributed to inherent differences in design and patient population. However, 90% response rates have never been reported in any of the LN studies. ASPREVA, in their clinical trial results, showed a 56% response rate with MMF and 53% with CYC. Each of the 370 LN patients was randomized to either a target MMF dose of 3 g/day or an IV CYC dose of 0.5 to 1 g/m² monthly for a 24 week induction period. The primary outcome was a specified decrease in urine protein-creatinine ratio and stabilization or improvement of serum creatinine [20]. The current standard of care treatment for SLE patients with Class III and Class IV glomerulonephritis consists of high doses of corticosteroids, accompanied by MMF. A summary of all these clinical trials is presented in Table 1.

For the current study background, induction therapy is suggested to be MMF with a target dose of 3g/day for 6 months. Based on the data from the published clinical trials summarized in Table 1, the expected complete response rate is predicted to be 20%. Clinical response (both complete and partial) is expected to be 50%.

Rationale for ACTH

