Recurrent renal flares cause renal damage leading to glomerulosclerosis and irreversible deterioration of renal function [9]. Safe and effective maintenance therapies are needed to prevent renal relapses, reduce progression to ESRD, and reduce the chance of adverse events. Clinical trials focusing on maintenance therapies by Contreras *et al.* [13], ALMS (Aspreva Lupus Management Study) [26] and Houssiau *et al.* (MAINTAIN) [27] suggest that MMF is at least equivalent to AZA for maintenance therapy. A summary of the maintenance trials is presented in **Table 3**. The current study patients will be maintained on MMF for total treatment duration of 2 years.

Non-immunomodulatory treatments are also used in the treatment of LN patients. These include ACE inhibitors, ARBs, and statins and are not restricted in this study.

C. RESEARCH DESIGN AND METHODS

Study Design

The study is a randomized, controlled phase IV, single center trial of ACTHar plus CellCept (Mycophenolate Mofetil), as defined by the ASPREVA Nephritis Trial (MMF 3000 mg daily) in the treatment of lupus nephritis. The primary outcome will be assessed at 6 months. Thereafter, subsequent therapy will be with CellCept maintenance 2000 mg daily.

Study Duration

Follow-ups for each patient will be conducted for a total of 24 months.

Primary Outcome

The proportion of participants who achieve a complete response at 6 months.

1. Complete response (CR) is defined as *all* of the following criteria having been achieved:
 - a. Stabilization of estimated glomerular filtration rate (i.e., a 6-month eGFR level \pm 10% of baseline) or improvement if the screening value is changed from patient's baseline
 - b. Inactive urinary sediment (red blood cells per high-power field [RBCs/HPF] <5-10, not due to gyn bleeding)
 - c. Urine protein/creatinine ratio <0.5

Secondary Outcomes

1. Frequency of responders = CR + Partial Responders (PR). PR = improvement from baseline of at least \geq 50% in all abnormal renal parameters (proteinuria and serum creatinine) without deterioration of any measurements at 6 months
2. Frequency of extra-renal flares as defined by the SELENA-SLEDAI Flare Index. Extra-renal disease activity measured by SELENA-SLEDAI and BILAG
3. Steroid -like side effects: increased in BP by 20 mmHg for both SBP and DBP, increased blood sugar with a fasting plasma glucose level \geq 126 mg/dl, weight gain \geq 10% of the initial weight, infections
4. Side effects

Inclusion Criteria

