Clinical response data will be evaluated every 3 months and reported as overall percent responders and complete and partial responders in each dosing arm. Also, side effects (including steroid-like side effects) will be evaluated every 3 months and reported to the IRB and Questcor. The observed response rates in this study will be compared to the historical expected complete response rate in LN of 20%, and total renal responses of 50%. A two-sided chi-square test will be used to compare the proportion of subjects with complete response and total responses between the treatment arms and these expected values. Differences in the baseline characteristic between the two treatment groups will be evaluated using descriptive statistics, the two-sample t-test for continuous variables and the chi-square test for categorical variables. Times to event for the endpoints of partial and complete remission will be analyzed with the use of the Cox proportional-hazards model. The proportion of SAEs in the study regimen will be compared with the expected SAEs from other lupus nephritis studies using a two-sided chi-square test at the 0.05 level of significance without using continuity correction.

The research will be conducted as per CUMC's strict guidelines, thus preventing unauthorized collection, use, and/or disclosure of data. Strict physical, technical, and administrative safeguards to protect data from unauthorized access and/or tampering will be in place. Appropriate measures to ensure confidentiality will be employed. The aggregate data will be entered in a database. The data will be kept in locked facilities that can only be accessed by study investigators or a member of the research team. This will be for a period of up to 10 years, after which the data collection forms and database from this study will be destroyed.

Sample Size Justification *Include power analyses or justification for enrollment plan*

N=10 patients per dosing arm.

References

2. Lam G, Petri, M: Assessment of systemic lupus erythematosus. *Clin Exp Rheumatol* 2005, 23:S120-S132.

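### With 10 patients per arm, the Cox model for complete remission has no finite hazard ratio in about one trial in five, and the partial-remission event is left undefined

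*Combined protocol and SAP*

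**What the plan says.** The Statistical/Analytical Plan gives time to response one sentence: "Times to event for the endpoints of partial and complete remission will be analyzed with the use of the Cox proportional-hazards model". It names no covariate, time origin, horizon, censoring rule, method for ties or fallback when an arm has no events. The same section says "Clinical response data will be evaluated every 3 months", and the Sample Size Justification consists of "N=10 patients per dosing arm".

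The expected rates come from the rationale for MMF as background therapy: "Based on the data from the published clinical trials summarized in Table 1, the expected complete response rate is predicted to be 20" per cent, and "Clinical response (both complete and partial) is expected to be 50" per cent. The analysis plan repeats both as historical comparators.

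Under Secondary Outcomes, item 1 reads "Frequency of responders = CR + Partial Responders (PR"), and PR requires at least 50% improvement "in all abnormal renal parameters (proteinuria and serum creatinine) without deterioration of any measurements at 6 months". Under Study Design, "The primary outcome will be assessed at 6 months", while Study Duration gives 24 months of follow-up. Patient Monitoring and Evaluation classes patients whose glucocorticoids are increased as non-responders.

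**The concern.** There are two separate problems.

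**Estimability.** A two-arm Cox model needs events in both arms to give a finite hazard ratio. At 20% CR, 10 patients per arm yield about 2 complete remissions per arm. An arm with none is a realistic outcome, and the plan does not say what would then be reported.

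**Meaning of the partial-remission event.** The responder definition adds CR and PR as categories, which makes it plausible that the partial-remission model counts PR only. On that reading, a patient who goes straight to CR never has the event. If one regimen turns partial into complete remissions, its PR-only hazard falls, and the better arm can show a hazard ratio below 1. In an open-label trial, leaving this choice until the data are in hand is undesirable.

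At stake is the only time-to-response analysis in the plan. The primary outcome is not affected.

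**Working it through.** The plan states no event count, hazard ratio or power for this analysis, so there is no figure to reproduce.

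**Inputs from the documents:** n = 10 per arm; CR 20%; CR + PR 50%, hence PR only 50% − 20% = 30%.

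**Assumptions:** remission means the response defined under the outcomes; 6-month horizon; arm as the only covariate; no dropout.

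**1. Chance of no finite hazard ratio.** An arm has no events with probability (1 − p)^10. With equal rates, at least one arm has none with probability 1 − [1 − (1 − p)^10]².

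- CR at 20%: 0.8^10 = 0.107, and 1 − 0.893² = 20.3%. Simulation of 20,000 trials agrees: 19.6% with visits at months 3 and 6, and 20.3% with continuous times.
- CR at 20% v 40%: 0.107 + 0.006 − 0.107 × 0.006 = 11.3%.
- PR only at 30%: 0.7^10 = 0.028, and 1 − 0.972² = 5.6%.
- PR or better at 50%: 0.5^10 = 0.001, and 1 − 0.999² = 0.2%.
- At least one of the CR and PR-only models: per arm 0.8^10 + 0.7^10 − 0.5^10 = 0.135, and 1 − 0.865² = 25.1%.

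Sensitivity of the CR figure:

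| Setting | No finite HR |
|---|---|
| 15% in both arms | 35.5% |
| 20%, 9 evaluable per arm | 25.0% |
| 20%, 8 evaluable per arm | 30.7% |
| 30% in both arms | 5.6% |
| 40% in both arms | 1.2% |

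**2. Information when the model can be fitted.** With 2 complete remissions per arm, the standard error of the log hazard ratio is roughly √(1/2 + 1/2) = 1, so the 95% interval spans a factor of about e^1.96 = 7.1 each way. By the Schoenfeld formula at a two-sided 0.05 level (assumed, since the plan gives none for this model), 4 events give about 10% power for HR = 2: √4 × ln 2 / 2 − 1.96 = −1.27.

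**3. Direction of a PR-only model.** Take constant competing hazards over 6 months, so that the PR hazard is −ln(1 − CR − PR)/6 × PR/(CR + PR). Assume CR 30% and PR 20% in arm A, and CR 20% and PR 30% in arm B. Total response is 50% in both.

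- PR only, CR patients censored: the total hazards are equal, so HR = 0.20/0.30 = 0.67.
- PR only, CR patients kept at risk: HR ≈ ln 0.8 / ln 0.7 = 0.63.
- PR or better: HR = 1.0.
- CR: HR = 0.30/0.20 = 1.5.

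The arm with more complete remissions looks worse only in the PR-only model.

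**4. When there is no penalty.** With CR 40% v 20% and PR 30% in both arms, the PR-only HR is 1.24 with CR censored and 1.00 with CR kept at risk. If the CR hazard doubles and the PR hazard is unchanged, the HR is 1.00 with CR censored. It drops to about 0.87 only if CR patients stay in the risk set, because the proportion with PR then falls from 30% to 26.6%.

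**The case against.** **The failure rate belongs to one model.** A reader might infer that both Cox models fail in one trial in five. They do not: 20.3% applies to CR, 5.6% to PR only and 0.2% to PR or better. Failure here means no finite hazard ratio or Wald interval. The score (log-rank) test can still be computed unless both arms have no events, which for CR has probability 0.107² = 1.15%. This stands in full.

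**The horizon is not stated.** Follow-up runs to 24 months. Three-monthly evaluation would then give up to eight event times instead of two, and later remissions would lower the 20%. The documents give no 24-month CR rate, so the size of the reduction is unknown. This stands as a limit on the figure.

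**The plan does not say that partial remission excludes CR.** A reader might infer that CR patients are censored in the partial model, but no such rule appears. Inclusion Criteria require a urine protein/creatinine ratio above 1 and CR requires one below 0.5, so every CR has more than halved the entry ratio. Most such patients would also meet the proteinuria part of PR. The nesting is incomplete, because CR accepts a stable eGFR while PR asks for improvement in an abnormal creatinine. The supportable criticism is that the event is undefined and that the responder definition makes a PR-only reading plausible.

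**The analysis is secondary.** Time to remission is not among the listed primary or secondary outcomes, and response percentages by arm are already to be reported every 3 months. This stands, and it limits the severity.

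**Conclusion.** The concern holds as a minor point about a secondary analysis. Given the assumptions set out above and the plan's 20% CR rate in both arms, the complete-remission model yields no finite hazard ratio in about 20% of trials. That falls to 11% if one arm reaches 40%, and rises to 25% with 9 evaluable patients per arm. The plan provides no alternative for that case.

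The partial-remission event is undefined. If PR only is used, a shift from partial to complete remission at constant 50% total response gives a PR-only HR of about 0.6 to 0.67 for the arm with more complete remissions. The rates behind that example (CR 30%/PR 20% v CR 20%/PR 30%) are assumed for illustration.

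It would be wrong to conclude that the plan penalises any arm with more complete remissions. That needs both a PR-only event and a fall in PR as CR rises, and the documents establish neither.

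**What to change.** Replace the Cox sentence with a short specification:

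1. Two endpoints, time to first response (PR or better) and time to CR, with the horizon and assessment visits stated. The first is non-estimable in only about 0.2% of trials.
2. Patients classed as non-responders under Patient Monitoring and Evaluation (glucocorticoid escalation) stay in the risk set without an event to the end of the window and are not censored. That passage does not cover other withdrawals, so their handling needs its own stated rule.
3. Cumulative response by visit and arm with exact 95% confidence intervals, and a permutation log-rank p-value for the comparison of arms. The exact interval remains usable with no events: for 0 of 10 its upper limit is 1 − 0.025^(1/10) = 30.8%.
4. If a hazard ratio is wanted, Firth-penalised Cox with a profile-likelihood interval.

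The cost is a few sentences of analysis wording and standard software, with no change to patients, visits or sample size. The downside is that there is no conventional Cox hazard ratio as a headline. These changes remove the undefined result and the ambiguity, but they do not make up for the small number of events.

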Open-label Prospective Randomized Study to
Determine the Efficacy and Safety of Two Dosing
Regimens of ACTHar in the Treatment of Proliferative
Lupus Nephritis

NCT02226341

January 3, 2024

Study Title**ACTHar in the treatment of Lupus Nephritis**

Principal Investigator: *[name] [name]*

Institution and department: *CUMC, Rheumatology*

A. SPECIFIC AIM

Start with a concise summary of the overall project (a few sentences). Please include hypotheses for each endpoint (see Section C) and provide rationale in Section B.

Open-label prospective randomized study to determine the efficacy and safety of two dosing regimens of ACTHar in the treatment of proliferative lupus nephritis. The treatment of lupus nephritis (LN) has remained mostly unchanged for many decades: High doses of steroids are still the cornerstone of LN therapy despite their devastating side effects. It is only recently that attempts at changing the requirements regarding steroid use have been made. The current proposal will evaluate the role of ACTH in the form of ACTHar gel in the treatment of proliferative LN. While we expect that a part of the therapeutic effects of ACTHar in LN will be mediated through the endogenous production of steroids, we hypothesize that a larger portion of the ACTH benefit may be due to the direct anti-inflammatory and reno-protective effect of ACTH dependent on the activation of the melanocortin receptors, rather than steroid production.

Accordingly, we propose that this study will evaluate the most effective dose of ACTHar gel in proliferative LN (Class III and IV) that produces the least steroid-like side effects, comparing two doses of ACTHar in conjunction with Mycophenolate Mofetil (MMF); MMF, in conjunction with Prednisone, is considered the current standard of care for LN. The dose of ACTHar was inferred based on the positive results of a study of membranous nephropathy. The primary outcome is renal response. Secondary outcomes are overall lupus activity and steroid side effects.

B. BACKGROUND AND CLINICAL SIGNIFICANCE**Introduction**

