Systemic lupus erythematosus (SLE) is an autoimmune disease of unknown etiology that mainly affects females of childbearing age. The disease is characterized by immune activation and the development of autoantibodies—particularly to double stranded DNA (dsDNA)—which are thought to be involved in tissue damage [1, 2]. Additionally, about 50% of SLE patients experience inflammation of the kidneys. LN is a major cause of morbidity and mortality in patients with systemic lupus erythematosus (SLE). Treatment of lupus nephritis is traditionally considered in two phases, induction and maintenance. Induction is aimed at reversing the immune-mediated inflammatory processes with high doses of immunosuppressives or cytotoxics in conjunction with high dose glucocorticoids (1mg/kg). Maintenance therapy is intended to assure durability of response and prevent recurrences using lower and presumably safer levels of immunosuppressive medications. Despite this aggressive therapy, 50% of patients do not achieve remission within 6 months [3]. Even if treatment is continued for 24 months, approximately one-third of SLE patients have an inadequate response [1, 3, 4]. Moreover, serious adverse events (SAEs) are common, especially with long-duration therapy. Complications of high-dose corticosteroid therapy in SLE patients include osteoporosis, aseptic necrosis, hypertension, diabetes, opportunistic infection, and cataracts. MMF therapy for lupus nephritis also causes serious adverse effects, including opportunistic infection and cancer. Clearly, safer and more effective therapies are needed for SLE.

The SLEDAI-2K (SLE Disease Activity Instrument) defines significant proteinuria as more than 500 mg of urinary protein excretion over 24 hours and the BILAG-2004 (British Isles Lupus Assessment Group), as either newly documented proteinuria over 1 gram or significant increase from baseline [1, 2]. In clinical practice and for the current study, significant proteinuria is defined as a protein-creatinine ratio of over 1 on a 24 hour collection.

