Dose finding study of patients with a recent flare of LN, and biopsy proven LN (Class III, IV) treated with CellCept 3 grams daily and ACTHar gel 80 U biw or Acthar gel 80 U qod. The dose of 80 U biw was chosen based on the published literature in MN. However, in an attempt to improve outcomes we also suggest a higher dose of 80 U qod to be used for one month of "induction". Patients in the 80 U qod arm will be tapered to 80 biw after the first month of therapy. In all groups, patients can be on a prednisone dose of ≤ 20 mg prior to initiating therapy with CellCept or ACTHar. Based on the investigator's judgment, patients will be switched to oral prednisone for worsening lupus nephritis or extra-renal lupus. Patients will be maintained on ACTHar for a total of 3 months. Patients with partial response will be offered the option to continue ACTHar 80 U biw for a total of 6 months. Each dosing arm will include 10 patients.

Biomarkers

Patients whose renal biopsies are available (we expect that 80% of patients will have a biopsy done within 1 month of the screening visit) will have frozen sections stained for MCR using anti-MCR antibodies in the manner described by Gong [35]. Similarly, skin biopsy samples obtained at D 0 and week 24 will be stained for MCR. The readout of MCR activation by ACTH in the skin will be ICAM-1, VCAM1, mEPCR. Also, levels of ICAM-1, VCAM-1, and E-selectin will be evaluated in urine samples collected at D 0, weeks 4, 12 and 24. Our center has extensive expertise in the measurement of these cytokines. Our collaborator [name] will supervise the work of examining all biomarkers. We hypothesize that dermal and urinary biomarkers are likely to decrease faster in response to treatment with ACTHar as a consequence of the direct activation of the MCR.

Treatment Overview

Screening protocol –as per attached schedule of assessments

CONCOMITANT MEDICATIONS

Participants may receive all required and non-prohibited concomitant medications as clinically indicated. Prednisone in a dose of ≤ 20 mg daily is allowed at study entry, but should be tapered to below 10 mg daily as tolerated by week 24.

Prophylactic Medications

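### The only inferential safety analysis is a significance test of SAEs in 20 patients, with no margin or interval; exact confidence intervals would be a cheap improvement

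*Combined protocol and SAP*

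**What the plan says.** The study title sets the aim: "Open-label Prospective Randomized Study to Determine the Efficacy and Safety of Two Dosing Regimens of ACTHar in the Treatment of Proliferative Lupus Nephritis". Section A repeats it.

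For serious adverse events, the Statistical/Analytical Plan gives one analysis: "The proportion of SAEs in the study regimen will be compared with the expected SAEs from other lupus nephritis studies", by a "two-sided chi-square test at the 0.05 level of significance without using continuity correction". It gives no number or source for the expected rate, no counting window, no margin, no confidence interval and no power. It does not say whether the proportion counts patients or events, or how a non-significant result would be read.

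The rest of the safety plan is descriptive: "side effects (including steroid-like side effects) will be evaluated every 3 months and reported to the IRB and Questcor". The chi-square tests on the treatment arms are specified for response only.

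The whole of Sample Size Justification is "N=10 patients per dosing arm". Treatment Description agrees: "Each dosing arm will include 10 patients". The closest the documents come to an SAE rate is the remark in Section B that "serious adverse events (SAEs) are common, especially with long-duration therapy".

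**The concern.** A significance test against an expected rate can show that SAEs are clearly more (or less) frequent than expected. When it shows neither, it does not say how large an excess remains possible. With 20 patients that remaining range can be wide, and the plan has no margin or interval that would display it.

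The safety question is central here. Section A looks for the more effective of two doses with the fewest steroid-like effects. Every patient also takes MMF, for which Section B names opportunistic infection as a serious adverse effect. The protocol lists immunosuppression among the short-term effects of ACTH, and infections that can threaten life among the effects of prolonged use. If the p-value is the only inferential safety result, a report that SAEs did not differ from other studies could be given more weight than the data can bear.

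**Working it through.** **Inputs from the documents:** n = 10 per arm, so 20 pooled; two-sided 0.05; chi-square without continuity correction. No power or SAE rate is stated, so there is no figure of the plan's own to reproduce.

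**Assumptions:** expected rate p0 of 10% to 30%, with 5% to 40% as sensitivity; p0 treated as a fixed value; each patient counted once (at least one SAE or none); the study regimen read as both arms pooled. The rises of 1.5-fold and 2-fold are illustrative.

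**Method.** The test declares an excess when (x − n·p0)/√(n·p0·(1 − p0)) ≥ 1.96, where x is the number of patients with an SAE. The cut-off c is the smallest such x. The miss rate is P(X ≤ c − 1) for X ~ Binomial(n, p1), with p1 = 1.5·p0 or 2·p0.

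**Worked case, p0 = 20%, n = 20.** The expected count is 4 and the standard deviation is √(20 × 0.2 × 0.8) = 1.789.
- x = 7: (7 − 4)/1.789 = 1.68, p = 0.09, not significant.
- x = 8: (8 − 4)/1.789 = 2.24, p = 0.03, significant. So c = 8.
- True rate 40%: P(X ≤ 7) = 0.416.
- True rate 30%: P(X ≤ 7) = 0.772.

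**Pooled, n = 20:**

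| Expected rate | Cut-off | 1.5-fold rise missed | Doubling missed |
|---|---|---|---|
| 5% | 3 | 81.4% | 67.7% |
| 10% | 5 | 83.0% | 63.0% |
| 15% | 7 | 85.7% | 60.8% |
| 20% | 8 | 77.2% | 41.6% |
| 25% | 9 | 68.3% | 25.2% |
| 30% | 11 | 75.1% | 24.5% |
| 35% | 12 | 67.1% | 11.3% |
| 40% | 13 | 58.4% | 3.2% |

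Because the cut-off is a whole number of patients, the miss rate jumps between these steps. At p0 = 11.2%, x = 5 gives (5 − 2.24)/1.410 = 1.957, so the cut-off rises to 6 and a doubling is missed 72% of the time (1.5-fold: 90%). At p0 = 29.9%, x = 10 gives (10 − 5.98)/2.047 = 1.963, so the cut-off is 10 and a doubling is missed 13% of the time (1.5-fold: 60%). The ranges quoted in this point are for the five-point steps.

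**Per arm, n = 10.** Cut-offs at 10%, 20% and 30% are 3, 5 and 6. A doubling is missed 68%, 63% and 37% of the time.

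**Reference as a sample rather than a fixed value.** Against a comparison cohort of 71 to 370 patients (sizes that appear in Section B), a two-sample uncorrected chi-square misses a doubling about 21% to 73% of the time at expected rates of 10% to 30%.

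**What the interval shows.** The exact (Clopper-Pearson) 95% interval for 7/20 is 15% to 59%. With an expected 20% this count is not significant, yet a rate well above double the expected one is not excluded. Per arm, 4/10 against 20% gives (4 − 2)/√1.6 = 1.58, also not significant, with an upper limit of 74%.

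**The case against.** The strongest objection is that the plan draws no conclusion from non-significance. It says only that the proportions will be compared. A reader might infer that p above 0.05 would be taken as proof of safety, but the text does not say so. The point is therefore about what the planned result could support. It is not a contradiction in the document.

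A reader might also infer that the test would usually miss a doubling. The documents give no reference rate, and the calculation does not bear this out across the assumed range. At expected rates of 20%, 25% and 30% the pooled test detects a doubling more often than not (58%, 75% and 75%). Section B calls SAEs common and follow-up lasts 24 months, so a reference above 30% is possible, and there the miss rate is small. Failure more often than not holds for the 1.5-fold rise at every rate in the table, but for a doubling only at the lower rates.

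Nor does safety as a whole rest on one p-value. Steroid-like effects with numeric thresholds, infections and side effects are secondary outcomes, there is three-monthly reporting, and there are discontinuation criteria. The life-threatening infections are tied to prolonged use, while ACTHar is planned for 3 months, with an option of 6. All this stands, but none of these provisions is inferential.

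Finally, any reader could compute an interval from the reported count, and an interval adds no patients and no power. That is true. It also means that planning the interval costs almost nothing, and doing so fixes in advance which result the safety statement rests on.

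**Conclusion.** The point holds as a cheap improvement. The plan's only inferential safety analysis is a two-sided 0.05 test in 20 patients against a rate it does not state, and no margin or interval shows what a non-significant result leaves open.

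That conclusion does not depend on a particular reference rate, but its size does. With expected rates of 10% to 30% in five-point steps, a fixed reference and patients as the counting unit, the pooled test misses a 1.5-fold rise about 68% to 86% of the time and a doubling about 25% to 63%. For a doubling, the figure is about 68% at an expected 5% and 3% to 11% at 35% to 40%. If events rather than patients are counted, these binomial figures do not apply.

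**What to change.** In the Statistical/Analytical Plan, make estimation the basis of the safety statement. Suggested wording:

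> The number and proportion of patients with at least one SAE will be reported per arm and pooled, each with an exact (Clopper-Pearson) 95% confidence interval. The safety statement will be based on the interval, with its upper limit set beside the expected rate of [value], taken from [source] over [time window]. Any p-value against the expected rate is descriptive. A non-significant difference will not be interpreted as evidence of safety or of equivalence to other regimens.

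The sponsor has to fill in the expected rate, its source and its window, because the documents supply none of them. The wording also settles that patients are the counting unit.

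The cost is a few sentences and three intervals, with no added patients, visits or data. The downside is a less favourable safety statement. Even with no SAEs, the one-sided 95% upper bound is 1 − 0.05^(1/20) = 14% for 0/20 and 1 − 0.05^(1/10) = 26% for 0/10. The two-sided 95% interval in the wording above reaches 1 − 0.025^(1/20) = 17% and 1 − 0.025^(1/10) = 31%.
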